All study participants completed informed consent documents before study participation and all who completed the full intervention and the interviewer-administered surveys received \$85 in gift card incentives. Data were collected via surveys from Cohort 1 immediately before the CIS (“intervention baseline survey”), 8-9-weeks after the CIS at posttest (“post-program survey”), and 6-month follow up (“follow-up survey”). For Cohort 2, survey data was collected at baseline (“control baseline survey”), an average of 13 weeks immediately before CIS attendance (“intervention baseline survey”), and an average of 12-weeks after the CIS (“post-program survey”). The first survey administered with Cohort 2 participants occurred at study enrollment and served as a control baseline comparison to Cohort 1.

Measures

ACP barriers and facilitators were assessed with 16 yes/no questions (8 barriers and 8 facilitators) derived from qualitative data regarding ACP and developed during the original MY WAY clinical trial, but never published.

ACP readiness and self-efficacy were captured with the 9-item ACP Engagement Survey Process Measures identified from Behavioral Change Theory. The 6-item readiness and

the 3-item self-efficacy subscales have 5-point, Likert responses of “not at all, a little, somewhat, fairly, extremely.” In a field test of these subscales, they demonstrated good reliability and discriminant validity (Sudore et al., 2017; 2013).

For **ACP completion**, participants were asked if they had a legal advance directive. To confirm self-reports post-program, project staff documented whether the participant’s advance directive was notarized after SS and compared this to notary records. All sources of the participant’s advance directive completion measure were combined into a single binary variable (yes/no).

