Interview-administered intervention and control baseline surveys also included self-reported demographic characteristics of age (in years), gender (male or female), marital status (married or not married), Tribal affiliation (member, first descendent, family of a member, member of another Tribe), education (on a scale of 1 = less than high school education to 5 = graduate degree), self-rated health (on a scale of 1 = very poor to 6 = excellent), and self-reported diagnosis of any chronic conditions. Chronic conditions included chronic obstructive pulmonary disease, history of stroke, history of heart attack, cancer, chronic kidney disease, type 2 diabetes, heart disease, high cholesterol, and chronic pain.

Analyses

All analyses were conducted in IBM SPSS Statistical Software (27) or Microsoft Excel. We examined participant demographic characteristics using descriptive statistics and stratified analyses. To determine if there were demographic or other differences between the cohorts, we conducted crosstabulation analyses with Bonferroni correction applied. To compare intervention baseline and post-program levels of barriers and facilitators, as well as analyze change over time in ACP readiness, self-efficacy, and completion, we combined the cohorts. As barriers and

facilitators were asked as simple “yes/no” questions, the number of barriers and facilitators listed by participants was calculated before and after the intervention for comparison.

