Before combining the individual readiness and self-efficacy items, we ran selectivity and reliability analyses. To check for differences in the sample due to attrition, we computed Little's missing completely at random (MCAR) test. We then conducted crosstabulations again to look for relationships between demographic characteristics and ACP readiness, self-efficacy, and completion measures at intervention baseline. With our combined sample, we conducted a 3 (readiness, self-efficacy, and completion) x 2 (pretest to 8-week posttest) way repeated measures analysis of variance (ANOVA) with demographic characteristics found to be related to intervention baseline measures as between-subjects variables. For 6-month follow-up surveys with Cohort 1, we conducted a separate one-way ANOVA (intervention baseline, post-program, follow-up) for ACP readiness and self-efficacy. We tested the hypothesis that Cohort 2 participants did not change ACP-related readiness and self-efficacy from control baseline to intervention baseline by conducting a third separate one-way repeated measures ANOVA. We also calculated difference scores from control baseline to intervention baseline among Cohort 2 participants and intervention baseline to post-program among all participants.

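### Little's test on attrition leads to no stated action, and the 3 x 2 ANOVA implies a complete-case analysis that can also discard completion data held in records

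*Combined protocol and SAP*

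**What the plan says.** The combined document deals with attrition in one sentence of the Analyses section: "To check for differences in the sample due to attrition, we computed" Little's test. No threshold is given, and neither result leads to a different step. The text then moves to crosstabulations of demographics with baseline measures, and the ANOVAs follow unconditionally.

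The change analyses are:

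- Both cohorts combined: "we conducted a 3 (readiness, self-efficacy, and completion) x 2 (pretest to 8-week posttest) way repeated measures analysis of variance (ANOVA".
- Cohort 1 at 6 months: "we conducted a separate one-way ANOVA (intervention baseline, post-program, follow-up) for ACP readiness and self-efficacy".
- Cohort 2 during the wait: change "from control baseline to intervention baseline by conducting a third separate one-way repeated measures ANOVA".
- Difference scores, including "intervention baseline to post-program among all participants". How people without one of the two surveys were treated is not stated.

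No section mentions imputation, a likelihood-based model, an analysed set, a missing-data sensitivity analysis or the number of people per survey. Study Aims gives 70 members without saying whether that is the number enrolled or analysed. Under Data Collection, "all who completed the full intervention and the interviewer-administered surveys received" the gift cards, so full participation was not taken for granted. Under Measures, completion is one yes/no variable that combines self-report with staff documentation and notary records.

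**The concern.** A classical repeated measures ANOVA needs every repeated value for each person, and a difference score needs both surveys. With no method named for gaps, the natural inference is that only people with complete surveys were analysed.

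Two consequences follow. First, the 3 x 2 model ties the outcomes together: someone who misses the post-program survey has no readiness or self-efficacy score and so leaves the completion comparison too, although completion may be on record. Second, the only named check on attrition is a test with limited power at this size, and it cannot detect drop-out that depends on unobserved change. If drop-out is related to baseline scores or to change, the estimates for all three outcomes may be biased in either direction, and a reader has no counts from which to judge it.

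**Working it through.** The documents state no attrition rate, SD, effect size or power, so there is no figure of theirs to reproduce. The only documented input is 70 people. Everything else here is assumed: attrition of 10/20/30% (leavers/stayers 7/63, 14/56, 21/49), correlations of 0.3-0.7, and the leaver-stayer differences shown.

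**1. Power of Little's test.** With post-program values missing for leavers, the test reduces to a 3-df Mahalanobis comparison of leavers and stayers on the three baseline outcomes, treated here as normal. Its noncentrality is (leavers x stayers / 70) x D². For example, with readiness alone 0.5 SD lower and correlation 0.5, D² = 0.25 x 1.5 = 0.375, and at 10% attrition the noncentrality is (7 x 63 / 70) x 0.375 = 6.3 x 0.375 = 2.36. Simulation with 20,000 runs per cell (null rejection 0.047-0.051) gives:

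| 0.5 SD lower in leavers | Correlation | 10% | 20% | 30% |
|---|---|---|---|---|
| Readiness only | 0.3 | 17% | 28% | 36% |
| Readiness only | 0.5 | 20% | 35% | 45% |
| Readiness only | 0.7 | 31% | 53% | 66% |
| All three | 0.3 | 25% | 44% | 55% |
| All three | 0.5 | 21% | 35% | 45% |
| All three | 0.7 | 18% | 29% | 38% |

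At 0.8 SD, power runs from 38% (10% attrition) to 98%. Exact power depends on which variables were entered, which the text does not say. A plain two-group comparison of means gives a similar picture: 24/39/48% at 0.5 SD and 52/76/87% at 0.8 SD.

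**2. Bias from drop-out explained by the intervention baseline score.** If leavers start 0.5 SD lower, complete-case bias in mean change is -(1 - r) x 0.5 x p, where r is the baseline-post correlation and p the attrition.

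- r = 0.5: -0.025, -0.05, -0.075 SD.
- r = 0.3 at 30%: -0.105 SD. r = 0.7 at 10%: -0.015 SD.
- SE of mean change = sqrt(2(1 - r)) / sqrt(stayers); at r = 0.5 this is 0.126, 0.134, 0.143 SD.
- Bias/SE is 0.20, 0.37, 0.52, so a nominal 95% interval covers 94.5, 93.4, 91.8%.

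A three-occasion simulation (assumed cohorts of 35 and 35, correlation 0.5, gain 0.5 SD, drop-out by first survey score with a gap of about 0.48 SD, half of Cohort 2 leavers leaving in the wait; 1,500 runs per cell) gives complete-case bias of -0.01, -0.03, -0.04 SD, against 0.00 for a likelihood-based mixed model. Counting leavers as unchanged gives -0.06, -0.12, -0.18 SD.

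**3. Bias if leavers do not change.** If stayers gain 0.5 SD and leavers nothing, complete cases overstate the gain by 0.5 x p = 0.05, 0.10, 0.15 SD. Bias/SE is 0.40, 0.75, 1.05 and coverage 93.2, 88.4, 81.7%. The mixed model has the same bias; the no-change analysis has none. Here p must be the share of people who received the intervention but lack a post-program survey.

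**4. Completion.** Under the condition in step 3, a gain of g points among stayers is overstated by p x g: for g = 20-40, by 2-4, 4-8 and 6-12 points. For example, 17 gains and no losses in 56 stayers is 17/56 = 30.4 points; with 14 more people counted as unchanged it is 17/70 = 24.3 points. The exact McNemar p-value is the same, so the gain and its interval carry the information.

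**The case against.** Much of the opposing case stands.

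- **A reader might infer that Little's test was used to justify complete cases.** The text does not say that. It presents the test as a check for differences, and it also mentions selectivity analyses, undefined, which could include a leaver-stayer comparison. What remains is that no consequence and no missing-data method is stated.
- **A reader might count Cohort 2 members who left during the wait as a source of bias in pre-post change.** The hypothesis in Study Design concerns change after participation. Leaving out people who never received the intervention answers a different question (a different estimand) and is not in itself bias. They should be counted separately.
- **A reader might apply a six-value rule:** 1 - 0.98^6 = 11.4% (8.0 of 70) to 1 - 0.95^6 = 26.5% (18.5 of 70) lost when 2-5% of values are missing. This treats completion as independently missing although records supply it, and if whole surveys are missed there is no such extra loss.
- **A reader might say that a missing 6-month survey removes a Cohort 1 member's pre-post change.** That ANOVA is not labelled repeated measures, and the same people can still enter the combined ANOVA and the difference scores.
- **The mixed model gains little.** In the simulation it removes 0.01-0.04 SD, and nothing if leavers do not change.
- **The aims are feasibility and preliminary outcomes.** This lowers the priority.

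The objection does not reach the loss of recorded completion data through the joint model, or the absence of any count by survey.

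**Conclusion.** The point holds in a limited form. The attrition check has no stated consequence, no missing-data method is given, and complete-case analysis is a fair inference but not a documented fact. The clearest defect is that completion, partly obtainable from records, is tied to survey scales that are not.

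Whether the results are materially biased cannot be determined. At correlation 0.5 and the assumed attrition, drop-out explained by observed scores costs about 0.01-0.08 SD, roughly half a standard error at most. The larger figure reaches about one standard error only at 30% attrition with no change in any participant who missed the post-program survey. If few surveys were missing, the effect is negligible. A non-significant Little's test would not settle the matter: even a 0.8 SD difference can go undetected with 10% attrition. Priority is minor to moderate.

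**What to change.** 1. Beside the ANOVAs already run, and labelled post hoc, analyse readiness and self-efficacy separately with a likelihood-based linear mixed model (SPSS MIXED, in the package already named) on all available surveys. Fit Cohort 1's three surveys in a separate model: nobody has both a control baseline and a 6-month survey, so a four-occasion unstructured covariance is not identified. State that these models address only drop-out explained by observed scores.
2. Take completion out of the 3 x 2 ANOVA and analyse it as a paired binary outcome, using staff and notary records even where the post-program survey is missing. Report the gain in points with a 95% CI, plus a sensitivity analysis counting unknowns as unchanged from baseline. That rule also covers people who have no notarization record because they never reached a Sharing Session.
3. For readiness and self-efficacy, show a no-change analysis for participants who began the intervention but lack post-program scores. Present it as a cautious bound and not a correction, since it understates the gain by 0.06-0.18 SD in the simulation of observed-score drop-out.
4. Report numbers and leavers' baseline characteristics by cohort and survey, separating those who left before the intervention from those who left after it. Do not use Little's test to support complete-case results.

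No new data are needed. The cost is a little more analysis work, post hoc status for the new models, and possibly slightly smaller reported effects. If only one step is taken, step 4 is the cheapest and would show whether the rest matters.

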Study Protocol and Statistical Analysis Plan

Culturally Tailoring an Advance Care Planning Intervention for American Indians

ID: 1685879-1

June 30, 2024

Study Aims

This project had three specific aims: 1. Culturally tailor the content of the Make Your Wishes About You (MY WAY) ACP curriculum and guide for one American Indian Tribe; 2. Assess the feasibility of the culturally tailored MY WAY ACP curriculum and patient education guide with the tribe; and 3. Examine the preliminary outcomes of the culturally tailored MY WAY ACP curriculum guide with 70 tribal members.

Study Protocol

Study Design

We used a quasi-experimental waitlist-controlled study design to test the hypothesis that after participating in the tailored MY WAY intervention, participants would experience decreased ACP barriers and increased ACP facilitators, readiness, self-efficacy, and completion. This design split our total participant pool into two cohorts to allow for a comparison group while still providing the intervention to all participants. Cohort 1 received the intervention immediately after study enrollment and served as the intervention group. Results from Cohort 1 were then compared to the waitlisted cohort, or Cohort 2, who waited over 3 months on average to receive the intervention.

Intervention

The intervention consisted of two steps: attendance at a Community Information Session (CIS) and attendance at an individual Sharing Session (SS).

Recruitment

Study eligibility criteria included being an enrolled Tribal member, spouse of a Tribal member, first descendant, or a member of another AIAN Tribe, aged ≥ 18 years, and residing within the Tribal service area. We recruited potential participants using convenience sampling

techniques. We made in-person study recruitment announcements at 13 Tribal venues and left flyers and hung posters at 26 locations. We also ran an ad in the Tribal newspaper and on three billboards. Tribal programs distributed MY WAY information on our behalf via their social media and/or email listserv. We also developed a project website and ran a short video on the local Tribal television station. Interested people were directed to call the Project Coordinator by telephone and/or speak with staff at a CIS and then screened for study eligibility and enrolled, if eligible.

Data Collection

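### The only pre-post test named for yes/no completion is a 3 x 2 ANOVA shared with two Likert scales, and no separate estimate or interval for completion is named

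*Combined protocol and SAP*

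**What the plan says.** Under Study Design, the combined protocol and SAP hypothesises that after the intervention "participants would experience decreased ACP barriers and increased ACP facilitators, readiness, self-efficacy, and completion". Completion is therefore a hypothesised outcome in its own right.

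Under Measures, readiness has 6 items, and "the 3-item self-efficacy subscales have 5-point, Likert responses", as do the readiness items. Completion is different in kind: all sources of the "advance directive completion measure were combined into a single binary variable (yes/no").

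Under Analyses, the cohorts are pooled for the pre-post comparison: to "analyze change over time in ACP readiness, self-efficacy, and completion, we combined the cohorts". The model named is a "3 (readiness, self-efficacy, and completion) x 2 (pretest to 8-week posttest) way repeated measures analysis of variance (ANOVA"), with baseline-related demographics as between-subjects factors. On scoring, the plan refers only to checks made "Before combining the individual readiness and self-efficacy items"; it does not say whether the items are averaged or summed.

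No other test of change in completion is named:
- The 6-month analysis covers two outcomes only: "we conducted a separate one-way ANOVA (intervention baseline, post-program, follow-up) for ACP readiness and self-efficacy".
- The Cohort 2 waitlist-period ANOVA also concerns readiness and self-efficacy only.
- The crosstabulations that include completion relate it to demographics at baseline, not to change.
- Difference scores are calculated, but their measures are not named and no test or interval is attached.

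**The concern.** The 3 x 2 label can be read in three ways.

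1. **Literal.** Outcome is a within-person factor with three levels. The time effect then averages raw changes in a 6-item score, a 3-item score and a 0/1 variable, and the interaction compares them. These have no common unit, so both results change with the scoring of the scales.
2. **Doubly multivariate.** The three changes are tested jointly. The result does not depend on scoring, but a significant result does not say which outcome moved.
3. **Shorthand** for a separate pre-post run on each outcome.

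Under the first two, a significant result could come entirely from the scales and still be taken as support for the completion hypothesis. Under the first, a rise confined to completion could also go undetected. Under the third, completion has its own test, but still no named effect estimate or interval. The reader cannot tell which of these a statement about completion would rest on.

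**Working it through.** The plan gives no power, alpha, effect size or result, so there is no figure to reproduce. The figures below illustrate how the named test behaves.

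**Inputs.** From the documents: n = 70 (target in Aim 3), 6 and 3 items, binary completion. Assumed: two-sided 0.05; item-mean SD 1; pre-post correlation 0.5; completion change independent of scale change; correlation rho between the two scale changes of 0 or 0.5; no between-subjects factors. Sums multiply item means by 6 and 3. Rates come from 20,000 simulated trials per scenario; the time effect is also worked by hand.

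**Formula for the time effect (literal reading).** Each person's score is the average of the three changes. The SD of a scale change is √(2 × (1 − 0.5)) × 1 = 1. With k = 1 and 1 for means, or 6 and 3 for sums, the variance of the average is (k1² + k2² + 2·rho·k1·k2 + Vc)/9, where Vc is the variance of completion change.

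**Scenario A: scales +0.3 points, completion flat at 20% with 8% gains and 8% losses (Vc = 0.16).**
- Means, rho 0: expected average 0.6/3 = 0.20; variance 2.16/9 = 0.240; SE √(0.240/70) = 0.0586; ratio 3.42; power about 92%.
- Means, rho 0.5: variance 3.16/9 = 0.351; SE 0.0708; ratio 2.82; about 79%.
- Sums, rho 0: expected average 2.7/3 = 0.90; variance 45.16/9 = 5.02; SE 0.268; ratio 3.36; about 91%. At rho 0.5, about 80%.
- Doubly multivariate (Hotelling T² on three changes): about 83% at rho 0 and 65% at rho 0.5, whatever the scoring.
- Completion alone: 2% (exact McNemar) or 4% (paired F), as it should be when nothing has changed.

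**Scenario B: scales flat, completion 20% to 50% with no losses (Vc = 0.3 − 0.3² = 0.21).** The expected average is 0.3/3 = 0.10 under either scoring.
- Means, rho 0: variance 2.21/9 = 0.246; SE 0.0592; ratio 1.69; about 38%.
- Sums, rho 0: variance 45.21/9 = 5.02; SE 0.268; ratio 0.37; about 7%.

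A 3 x 2 ANOVA also reports the interaction (here Hotelling T² on two contrasts), so both effects must be counted:

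| % significant, means / sums | rho 0 | rho 0.5 |
|---|---|---|
| Time | 38 / 7 | 28 / 6 |
| Interaction | 75 / 12 | 60 / 10 |
| Time or interaction | about 93 / 16 | about 81 / 15 |
| Doubly multivariate | 100 | 100 |
| Completion alone | 100 | 100 |

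The scoring matters because completion supplies 0.21/2.21 = 9.5% of the variance of the average with means, but 0.21/45.21 = 0.5% with sums.

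**Check under other assumptions.** Discrete simulated items, 10% baseline completion and 40% of non-completers converting give the same pattern with univariate F tests: time 69% with means and 10% with sums; interaction 93% and 10%. Coding items 0-4 instead of 1-5 changes neither the time nor the interaction result; only the unit matters.

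**The case against.** The strongest objection is that the label is shorthand. The plan calls the Cohort 2 analysis "conducting a third separate one-way repeated measures ANOVA", which might suggest that the 3 x 2 was counted as one model. The same count, however, includes a one-way ANOVA on two outcomes, and a one-way ANOVA over time has one outcome, so that entry must already stand for at least two runs. The count is therefore weak evidence for a pooled model. Under the per-outcome reading, neither the dependence on scoring nor the confusion between outcomes arises. This objection stands as a real possibility; the text does not settle it.

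A second objection is that the difference scores may already supply the estimate: the mean difference of a 0/1 outcome is the paired risk difference. That is possible, but completion is not named there and no interval is mentioned.

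A third is that this is a preliminary study. That limits the weight of any test, but an estimate with an interval serves a preliminary aim better than a joint p-value.

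A reader might go further and infer that the ANOVA would hide a real rise in completion. With mean scoring the model usually signals something (about 93% or 81% in scenario B), although it does not say which outcome moved. Severe masking occurs mainly with sum scoring, which the plan does not say was used, and a 30-point rise in completion with flat scales is an extreme case.

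A reader might also infer that an F test on 0/1 data is itself the fault. It does little harm. With 13 gains and 2 losses among 70, the paired F gives p = 0.0038 and exact McNemar p = 0.0074; the paired F's false-positive rate in scenario A is about 4%.

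**Conclusion.** The point holds in a limited form and is worth fixing. Whichever reading applies, the plan names no separate estimate or interval for a yes/no outcome that it hypothesises will increase. If the 3 x 2 is a joint test, literal or doubly multivariate, its significance cannot support a statement that completion rose: with scales +0.3 and completion flat, the time effect is significant in about 92% (79% at rho 0.5), against 2 to 4% for completion alone. Dependence on scoring, and the masking that can follow from it, belong to the literal reading only.

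The rates rest on the assumed SD, correlations, completion rates and independence listed above; only the 70 is from the documents. With 50 participants after attrition (also assumed), the scenario A time effect is still significant in about 81% (means) or 80% (sums) at rho 0, and 64% or 65% at rho 0.5. The demographic factors are not modelled. The documents contain no results, so nothing here shows that a reported finding is wrong.

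**What to change.** State which model was run, whether the scales are item means or sums, and how many participants have both surveys. Replace the joint 3 x 2 test with one analysis per outcome, comparing the intervention baseline survey with the post-program survey:

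- **Readiness and self-efficacy:** a paired analysis or linear mixed model, reporting mean change with 95% CI.
- **Completion:** the 2 x 2 table of gains and losses, the paired risk difference with 95% CI, and exact McNemar, or logistic GEE if the demographic covariates are kept.

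The Bonett-Price interval suits completion. With p1 = (gains + 1)/(n + 2), p2 = (losses + 1)/(n + 2) and d = p1 − p2, it is d ± 1.96 × √((p1 + p2 − d²)/(n + 2)). Two illustrations with n = 70:
- 21 gains, 0 losses: observed +30 points; p1 = 22/72, p2 = 1/72, d = 0.292, SE 0.057; interval 18 to 40 points.
- 13 gains, 2 losses: observed +16 points; p1 = 14/72, p2 = 3/72, d = 0.153, SE 0.054; interval 5 to 26 points. Exact McNemar p = 2 × (1 + 15 + 105)/2^15 = 0.0074.

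The cost is a wording change and a short re-analysis of data already collected. There are three tests instead of one; Holm across the three deals with this if error control is wanted. Exact McNemar is slightly conservative: for a rise from 20% to 35% with 3.5% losses and n = 70, power is about 74% against 81% for the paired F. The main gain is the separate estimate and interval, not the choice of test.

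### The Cohort 1 baseline, post-program and 6-month analysis is written as a one-way ANOVA without the repeated measures label; confirm which model was run and specify a within-person one

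*Combined protocol and SAP*

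**What the plan says.** The Analyses section of the combined protocol and SAP describes three ANOVAs in sequence.

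1. Combined cohorts, pretest to posttest: a 3 x 2 "way repeated measures analysis of variance (ANOVA) with demographic characteristics found to be related to intervention baseline measures as between-subjects variables".
2. Cohort 1 at three waves: "we conducted a separate one-way ANOVA (intervention baseline, post-program, follow-up) for ACP readiness and self-efficacy".
3. Cohort 2 over its waiting period: the no-change hypothesis is tested "by conducting a third separate one-way repeated measures ANOVA".

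The Data Collection section shows that the three levels of the second ANOVA are successive surveys of one cohort: "Data were collected via surveys from Cohort 1 immediately before the CIS", then 8–9 weeks after the information session, then at 6 months.

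For the second ANOVA the plan states no within-person factor, error term, sphericity correction or contrasts between waves. It also does not say how a participant without a 6-month survey is handled. Little's MCAR test is planned for attrition in general, but no rule follows from it for this model.

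**The concern.** Unqualified, one-way ANOVA ordinarily names the independent-groups test. Here the only factor is survey time and the same people answer at each level, so that test would have the wrong error term. Stable differences between people would stay in the residual, although they cancel out of each person's change.

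This is the only analysis in the document that uses the 6-month surveys. If the literal wording was followed, the study's only 6-month result for readiness and self-efficacy comes from an insensitive test, and a non-significant F would say little about whether scores moved.

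**Working it through.** The plan gives no alpha, power, SD, within-person correlation, effect size, Cohort 1 size or 6-month response, so it has no figure of its own to reproduce. The check asks what would follow if the literal reading was what was run.

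**Inputs**
- Waves: k = 3 (Analyses).
- Total sample: 70 (Study Aims: "Examine the preliminary outcomes of the culturally tailored MY WAY ACP curriculum guide with 70 tribal members"). Study Design says only "This design split our total participant pool into two cohorts", with no ratio. An even split gives 70/2 = 35 in Cohort 1. I assume n = 35, and n = 20 to allow for an uneven split or loss by 6 months.
- Assumed: normal scores with SD 1, equal correlation r between waves (0.3 to 0.7), nominal alpha 5%, complete data.
- Assumed effect: means 0, 0.4, 0.4 (a 0.4 SD gain held at both later waves).

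**Error terms**
- Independent-groups F: the error mean square has expectation σ², with df 3n − 3 (102 at n = 35; 57 at n = 20).
- Repeated measures F: the error mean square has expectation σ²(1 − r), with df 2(n − 1) (68 at n = 35; 38 at n = 20).
- With no change, the mean square for time has expectation σ²(1 − r) in both. The independent-groups F is therefore centred near 1 − r instead of 1, which makes it conservative.
- Half-widths of intervals for change are inflated by about 1/√(1 − r): 1.20 at r = 0.3, 1.41 at r = 0.5, 1.83 at r = 0.7.

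**Power of the repeated measures test (noncentral F)**
- λ = n Σ(μj − μ̄)² / [σ²(1 − r)].
- μ̄ = 0.8/3 = 0.267, so Σ(μj − μ̄)² = 0.0711 + 0.0178 + 0.0178 = 0.1067.
- n = 35, r = 0.6: λ = 35 × 0.1067/0.4 = 9.33; critical F(2, 68) = 3.13; power 77%.
- n = 20, r = 0.3: λ = 20 × 0.1067/0.7 = 3.05; critical F(2, 38) = 3.24; power 30%.

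**Simulation of both tests (40,000 data sets per setting)**

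| n | r | Type I error, independent groups | Type I error, repeated measures | Power, independent groups | Power, repeated measures |
|---|---|---|---|---|---|
| 35 | 0.3 | 1.4% | 5.0% | 33% | 51% |
| 35 | 0.4 | 0.9% | 5.1% | 30% | 58% |
| 35 | 0.6 | 0.13% | 5.0% | 25% | 77% |
| 35 | 0.7 | 0.01% | 5.0% | 22% | 88% |
| 20 | 0.3 | 1.5% | 4.9% | 17% | 31% |
| 20 | 0.6 | 0.12% | 4.8% | 9% | 49% |
| 20 | 0.7 | 0.03% | 4.9% | 7% | 62% |

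The smallest type I errors rest on a handful of rejections and should be read only as far below 0.1%.

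At r = 0 the two tests agree (n = 35: power 38% and 37%, type I error about 5% for both). The loss therefore comes entirely from ignoring the within-person correlation.

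A gain that is lost again by 6 months (means 0, 0.4, 0) has the same Σ(μj − μ̄)² and gives the same power to within simulation error. The test would miss a decline as readily as a sustained gain.

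**The case against.** The strongest objection is that the words were merely left out. The levels in brackets are survey times of a single cohort. The preceding sentence uses the repeated measures and between-subjects terms correctly. The next sentence calls the Cohort 2 test the third of its kind, which can be read as making the Cohort 1 test the second repeated measures ANOVA. One-way gives the number of factors, not the error structure.

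This stands to the extent that omission is a live reading. A reader might infer that the plan does treat the waves as independent groups, or that such a test was run; the documents establish neither. The ordinal does not settle the matter the other way. The first ANOVA is 3 x 2, so the Cohort 2 test cannot be the third one-way repeated measures ANOVA. The word may simply count ANOVAs.

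A reader might also infer that the flaw would specifically turn maintained gains into a finding of no maintenance. That goes too far. A three-wave omnibus F tests for any difference among waves; maintenance concerns the change from post-program to 6 months, for which the plan states no contrast. Short-term change also has its own test in the combined sample, explicitly repeated measures and unaffected by this point.

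Finally, the error would be conservative and the study is preliminary. Both are true, and they limit the harm to missed change and wide intervals.

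**Conclusion.** The concern holds as a point about specification. The wording of the only 6-month analysis, taken literally, names a test with the wrong error term, and nothing else in the document resolves it. Whether that test was run is unknown.

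If it was, then over the assumed range (n = 20 to 35, r = 0.3 to 0.7, 0.4 SD at both later waves) power is about 7–33% against 30–88% for repeated measures, and type I error runs from far below 0.1% to about 1.5% instead of 5%. Real change in either direction could be missed, and false positives are not inflated. If words were omitted, none of this loss occurred and only the text needs correcting. Cohort size, correlation, effect size and compound symmetry are assumptions, not document figures. At r = 0 the loss vanishes, and it grows with r.

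**What to change.** State which model was used for the Cohort 1 three-wave analysis, and replace the wording with a within-person model in which time is the repeated factor. There are two suitable choices:

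- a linear mixed model with participant as the repeated unit, using all available surveys, which also covers people who missed the 6-month survey; or
- a one-way repeated measures ANOVA with a Greenhouse-Geisser correction, stating how many participants have all three waves and how the others are handled.

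Report the changes from baseline to post-program, baseline to 6 months and post-program to 6 months for readiness and self-efficacy, each with a 95% CI. The last of these addresses maintenance directly.

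If an independent-groups ANOVA was run, rerun the analysis and replace the result. The cost is a wording change in the Analyses section and at most one rerun in the same software, with no new data.
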